**6) Study Endpoints**

**Primary:** The primary study endpoint will be the assessment of patient safety and comfort at the conclusion of the imaging phase of the study.

**Secondary:** The secondary study endpoint will be the comparison of breast MRI versus breast CT in terms of sensitivity and specificity using biopsy findings as the standard of truth for lesion characterization. True positives & negatives and false positive & negatives will be defined and ROC (receiver operating characteristics) curves will be generated.

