**7) Procedures Involved**

The patient's biopsy appointment typically occurs about 1 week after her diagnostic work-up in the Mammography clinic. Breast CT and breast MRI scans may take place on different days, or both may be done on the day of her biopsy appointment. Whichever is done first will depend on the clinical MRI clinic schedule. The second scan, whether it is breast CT or breast MRI, will take place prior to the subject's scheduled breast biopsy appointment.

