### Breast MRI:

The subjects will arrive at the Ambulatory Care Center, Suite 0500 on the day of their study breast MRI. After screening by an MRI technologist for MRI contraindications, an I.V. will be placed in the subject's forearm. The subject will then be positioned on the scan table prone, with each breast hanging into separate holes of the MRI coil. Pre-contrast scanning will then take place (short T-1 inversion recovery (STIR) and T-1 weighted pulse sequences). MRI contrast will then be injected (Omniscan (Gadodiamide) GE Healthcare) at a dose of 0.2 ml/kg and at a rate of 2 ml/second by a power injector. 15-20 ml of normal saline will be used as a flush. Post-contrast scanning will then take place. Following this, the subject's visit will be complete. Total time for this visit is approximately 45 minutes.

**NOTE:** If a subject wishes to participate, but cannot or will not, undergo MRI scanning, the subject may still be enrolled for the CT portion only.

After the scans have finished, the participant will be given a questionnaire to complete about their experience during the study. After completion of the scans and completing the questionnaire, their active participation in the study will be

completed. Access to their medical record for follow up information may continue.

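### Comfort, a named part of the primary endpoint, is collected once after the last scan, so ratings of breast CT are open to recall and scan-order effects and may not be separable from MRI

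*Combined protocol and SAP*

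**What the plan says.** Section 6 states: "The primary study endpoint will be the assessment of patient safety and comfort at the conclusion of the imaging phase of the study". It names no instrument, scale, summary measure or comparator for comfort.

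The only collection of comfort data that can be seen is at the end of the Breast MRI text in Section 7: "After the scans have finished, the participant will be given a questionnaire to complete about their experience during the study". Participation then closes: "After completion of the scans and completing the questionnaire, their active participation in the study will be" over. No form after each individual scan is described.

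On timing, Section 7 says "Breast CT and breast MRI scans may take place on different days, or both may be done on the day of her biopsy appointment". On order it says "Whichever is done first will depend on the clinical MRI clinic schedule". Both scans come before the biopsy, and "The patient's biopsy appointment typically occurs about 1 week after her diagnostic work-up in the Mammography clinic". A woman who cannot or will not have MRI may still take part: "the subject may still be enrolled for the CT portion only".

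**The concern.** Breast CT is the test under evaluation (Section 2). The MRI scanner is already in clinical service (Section 21). A comfort result is therefore useful mainly if it can be read as comfort during breast CT. Three features of the stated procedure work against that reading.

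- **Recall.** When CT comes first and MRI is on a later day, CT is rated from memory.
- **Order.** Some women rate CT just after having it and others rate it after an MRI in between. Scheduling decides which, and the text does not say that order will be recorded or tabulated.
- **Meaning.** A question about the study as a whole covers CT alone for CT-only women and two scans for everyone else.

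At stake is whether the comfort component of the primary endpoint can be attributed to the device. Ratings not taken at the CT visit cannot be recovered at the analysis stage.

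**Working it through.** The plan gives no comfort figure to reproduce. The sizing in Section 8 concerns reader-study AUC only. The check is therefore mainly a reading of the sections side by side.

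**1. One administration or two?** Section 7 refers to the scans in the plural, then one questionnaire, then the end of participation. Each visit is put at about 45 minutes, and 45 + 45 = 90 minutes, which is the 1.5 hours given in Section 5. That fits a single form at the end of two visits but does not prove it.

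**2. How long is the recall interval?** Both scans precede a biopsy that typically falls about 1 week after work-up. The gap between scans therefore runs from the same day to, typically, about a week at most.

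**3. Who rates what, and when?**

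| Group | Position of the form relative to CT | What a global item would cover |
|---|---|---|
| CT first, then MRI | After an intervening MRI, same day to about a week later | CT and MRI |
| MRI first, then CT | Straight after CT, with MRI already experienced | CT and MRI |
| CT only | Straight after CT | CT |

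The documents give none of the three group sizes.

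**4. Does the score mix the two scans?** That depends on the items, which are not in the available text. With separate CT and MRI items, mixing is zero. With a single global item, an illustration is possible under assumptions that do not come from the documents. Let w be the weight a woman with both scans gives to CT, c the share of CT-only women, and let mean CT comfort be the same in both groups. Then

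mean score = c·CT + (1 − c)[w·CT + (1 − w)·MRI] = CT + (1 − c)(1 − w)(MRI − CT).

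Reading that score as CT comfort is off by (1 − c)(1 − w) times the MRI-minus-CT gap:

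| w | c = 0 | c = 0.10 | c = 0.30 |
|---|---|---|---|
| 0.25 | 0.75 | 0.675 | 0.525 |
| 0.50 | 0.50 | 0.45 | 0.35 |
| 0.75 | 0.25 | 0.225 | 0.175 |

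The error also moves with c, so the study mean would depend on how many women skip MRI.

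**5. Which way would it go?** The documents do not settle this. Section 7 describes CT as uncompressed and, apart from noise, not felt. Section 12 lists claustrophobia as a common risk of MRI. It also lists nausea, vomiting and itching among the common risks of the iodine contrast used for CT, against only injection-site problems for gadolinium. A gap between the two visits is plausible, but its sign is open.

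**The case against.** The strongest reply is that the stated time point agrees with the endpoint. Section 6 places the assessment at the end of the imaging phase, and the questionnaire is given there. Section 6 does not say comfort of breast CT. That stands: the two sections do not contradict each other, and a reader who infers that the timing violates the endpoint definition goes too far. The CT focus comes from the study's purpose in Section 2.

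A reader might also infer that the comfort score mixes CT with MRI. The documents do not establish this. They describe one administration, not a global rating, and one form can hold separate items for each scan. The instrument may be in text that is not available. This also stands, so mixing can be put only conditionally.

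Further limits are fair. Recall is short. No CT-versus-MRI comfort comparison is planned, so scan order confounds no stated contrast. No comfort hypothesis or threshold is given, so no stated decision would change. The safety component does not depend on the form: a physician attends the contrast scans (Section 12) and adverse events are reported separately (Section 10).

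What the reply leaves untouched is the timing. Even with separate items, women who have CT first rate it after MRI, those who have MRI first rate it at once, and scheduling decides the split.

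**Conclusion.** The point holds as a cheap improvement in measurement, not as an error in the plan. Followed as written, women with both scans may rate breast CT after an intervening MRI and up to about a week later, while CT-only women rate CT alone. That exposure exists whatever the items say. Loss of attribution to breast CT follows only if the items are global.

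The size and direction cannot be computed from the documents. The range of 0.175 to 0.75 of the gap rests on assumed weights of 0.25 to 0.75, an assumed CT-only share of 0 to 0.30, and a global item; with separate items it is zero. It would be wrong to conclude that CT comfort is understated by some number of points, because the documents give no scale, score or sign for the gap.

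**What to change.** In Section 7, give the short questionnaire at the end of each scan visit, before the woman leaves, and record CT and MRI answers separately. Report the CT-visit answers as the breast CT comfort result. An end-of-imaging summary can be kept alongside if wanted, so that the wording of Section 6 is still met. Record scan order and both scan dates, tabulate comfort by order, and show CT-only women separately.

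If the existing form already has separate items, say so in the protocol. That removes the mixing concern, and the form at each visit then deals with recall and with any effect of a later MRI on the CT rating. An MRI done before CT can still colour the CT rating, which is why order should be tabulated.

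The cost is one extra short form for each woman who has both scans, with no extra visit. The change has to be in place before the data are collected.

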## **8) Data and/or Specimen Management and Confidentiality**

Statistics and Determination of Study Sample and Data Analysis:

For this next cohort of 400 subjects, the following statistical analysis has been performed:

Over the past three years, the UC Davis breast imaging facility has averaged 15,818 screens, 2,665 diagnostic exams, and 480 biopsies annually. Patient recruitment will be ongoing during the first 4 years of the proposal, so that a “forgetting” time of at least 6 months can be enforced from the time of imaging to the reader studies. All cases will be recruited from BIRADS 4 & 5 women who will be biopsied in our facility, and we assume the historical 38% positive biopsy rate for our facility. The recruited women will undergo pre- and post- contrast bCT imaging, as well as pre- and post- contrast CE-MRI imaging. These women will all have had bilateral 2D and 3D mammography imaging as part of their screening and diagnostic workup. The biopsy findings will serve as ground truth for all cases. In addition, the vast majority of women will have all findings limited to a single breast, leaving the unaffected breast available as a non-cancer image (i.e. normal) for the screening study in Aim 4. Based on the power studies described below, the minimum number of women we need to recruit to run the study is 150 with biopsy-verified cancer and an additional 50 with benign findings (i.e.,  $150 / 0.38 = 395 \approx 400$ ). At a minimum, we plan to recruit 400 and will strive to recruit substantially more. Given a total of 1,920 candidate women, the 38% positive rate for biopsy, and a 25% rate of recruitment, we would expect to be able to acquire 182 cases ( $1920 \times 0.38 \times 0.25$ ) with cancer over the recruitment period, and this would correspond to  $\sim 298$  ( $1920 \times 0.25 \times [1-0.38]$ ) women with benign findings.

These recruitment figures are conservative in terms of the recruitment rate, and they still provide more than enough cases for our studies.

Numbers of patients needed: To size the studies, we have conducted power analyses [Abbey et al., 2013] based on the Roe and Metz simulation (2,000 runs) for a fixed effects ANOVA model instead of the usual mixed effects model proposed by Dorfman, Berbaum, and Metz (DBM) or correlated error model of Obuchowski and Rockette (Hillis SL, et al., 2005). For the normal-risk bCT-screening study (Aim 4), we have sized the study on the basis of 4 readers, an improvement of 0.05 in AUC, and with average AUC near 0.85 (i.e. AUC = 0.825 vs AUC = 0.875). At these performance benchmarks, 82% power is achieved with 150 positive cases and 250 negative cases. This is a reasonable number of cases given the recruitment procedures described in §D3.1. For the CE-bCT/CE-MRI (high risk screening) comparison (Aim 5), we investigate the non-inferiority of breast CT relative to MRI. We will consider breast CT to be successful in the pilot study if the observed difference in reader-averaged AUC values is greater than -0.025 (i.e.  $AUC(BCT) - AUC(MRI) > -0.025$ ), for a study in which average AUC is approximately 0.85. The Roe and Metz simulation [Abbey, et al, 2013] with 4 readers and 150 cases (60 positive and 90 negative) yields 82% power for finding non-inferiority as defined above in 2,000 independent simulation runs. We expect to be able to recruit at least this many patients for this study based on the recruitment procedures described above.

Informed consent and subject accountability:

There will be a clear accounting of all subjects involved with the study. This includes subjects who are consented, screened, eligible and enrolled as well as ineligible subjects. If a candidate is deemed ineligible for enrollment, the reason for ineligibility will be recorded. There will also be a listing of all patients discontinued or withdrawn from the study after enrollment. These statistics will be reported to the IRB during annual reviews when required.

All subjects participating in this study will provide written consent in the form of the Informed Consent Form. The investigators will allow the candidate to read the consent form and will ask the candidate if they have any questions prior to enrollment. Subject initials, signatures, and date and time will be required in the appropriate places on the form.

Data Handling and Data Management:

The data from all subjects will be used in the safety and efficacy evaluation. Documentation containing the subjects' Protected Health Information (medical history, mammograms, ultrasound images, Breast CT images, breast MRI images,

biopsy reports) that is collected for research purposes will remain in the custody of study personnel (kept in a secure location), and will not be copied or discarded. This documentation will be de-identified after the data has been analyzed and the results are ready for publication.

Source documentation will be identified by ink stamp which will include the initials of the study personnel recording the data and the date on which it was recorded.

Written corrections to source documents will be made in the following manner: the corrected information will be written next to the information being corrected, and the information being corrected will be crossed out with a single line and the investigator's initials and the date of the correction will be written next to the lined out information.

Records Retention:

All source documentation pertaining to the conduct of this study will be retained by the investigator for a period of 5 years following the closure of the study. This documentation includes screening mammography images, mammography exam reports, breast CT images, digital image data files, case report forms, biopsy reports, IRB correspondence and approvals, informed consent forms, urine pregnancy test reports, protocol deviations, and adverse event reports.

Documentation containing the subjects' Protected Health Information (name, medical record number, medical history) that is used for recruitment purposes will remain in the custody of study personnel, and will not be copied or discarded. No identifiers, used for recruitment purposes, will be disclosed to a third party except as required by law or for authorized oversight of the research project.

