**Specific Aim 3: Clinical Trial: Imaging women using breast CT and CE-MRI**  
Women with suspicious lesions (BIRADS 4+5) will undergo digital mammography ("2D") and tomosynthesis ("3D") as standard of care workup. Patients who participate will undergo both unenhanced and contrast enhanced breast CT imaging, and also contrast-enhanced breast MRI. Both breasts (affected and unaffected) will be imaged with bCT and MRI. Our facility biopsies 2400 patients over 5 years, and power analysis shows that we will need a total of 400 patients whose images will be used for the normal-risk patient screening comparisons (Aim 4) and for the high risk patient screening comparisons (Aim 5).

**Specific Aim 4: Normal Risk Screening Performance: Comparison of non-contrast bCT with 2D and 2D+3D mammography.** The 4th bCT scanner ("Doheny") is now operational and has four times the spatial resolution of our earliest scanner. Non-contrast bCT has demonstrated better mass-lesion detection performance than mammography (Lindfors, et al, 2008) but using the earlier bCT systems, microcalcification detection was inferior to mammography. Doheny now has vastly improved spatial resolution, and we hypothesize that bCT is (now) equal to or better than screening mammography for microcalcification detection. In this aim, digital mammography and non-contrast bCT images will be compared in a standard receiver operating characteristic (ROC) study. Mammography with Tomosynthesis will also be compared against non-contrast bCT, using ROC methods. A full-search methodology will be used.

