### **13) Potential Benefits to Subjects**

Breast CT images will not be used for diagnosis or treatment planning, and will provide no direct benefit for subjects. Breast MRI scans are the imaging Gold

Standard for breast lesion clinical diagnosis, and the MRI scans performed for this study will be interpreted by a radiologist with the reports available in the subject's medical record. These findings will be available to the subject's referring or primary care physician.

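### Aim 4 may count an unbiopsied opposite breast as a normal negative with no rule for confirming it, and the make-up of the 250 negatives is not stated

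*Combined protocol and SAP*

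**What the plan says.** All references are to the combined protocol and SAP.

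- **Truth standard.** Section 8, in the statistics text, says: "The biopsy findings will serve as ground truth for all cases". Section 6 is narrower: there biopsy is the standard for characterising lesions in the MRI versus CT comparison.
- **Opposite breast.** Section 8 then expects findings in one breast only for most women, "leaving the unaffected breast available as a non-cancer image (i.e. normal) for the screening study in Aim 4".
- **Work-up.** On mammography, section 8 says: "These women will all have had bilateral 2D and 3D mammography imaging as part of their screening and diagnostic workup". Under Specific Aim 4 in section 2, "digital mammography and non-contrast bCT images will be compared in a standard receiver operating characteristic (ROC) study", with full search; tomosynthesis is compared as well.
- **Recruitment.** The section 8 minimum is "150 with biopsy-verified cancer and an additional 50 with benign findings", which the same sentence equates with 150/0.38 = 395, rounded to 400. Next comes "At a minimum, we plan to recruit 400". At a 25% recruitment rate the section expects 182 women with cancer and about 298 with benign findings.
- **Power.** For Aim 4, with 4 readers and AUC 0.825 versus 0.875, "82% power is achieved with 150 positive cases and 250 negative cases".
- **Other information on the opposite breast.** Specific Aim 3 images both breasts with bCT and MRI. Section 13 says "the MRI scans performed for this study will be interpreted by a radiologist with the reports available". Section 7 allows enrolment for CT only and says that record access may continue after the scans. Section 5 gives about 2 to 3 months of pathology follow-up.

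**The concern.** A truth standard of biopsy for all cases cannot apply to a breast that was not biopsied. That the opposite breast normally has no biopsy is an inference, but it follows from findings being confined to one side. Nothing in the available text fills the gap. The MRI report, the pathology follow-up and the continued record access are never made conditions for the normal label, and MRI is not compulsory.

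What marks the breast as unaffected is the clinical work-up, which includes bilateral mammography. The label is therefore not independent of a test being compared in Aim 4. A cancer in that breast would enter the ROC analysis as a negative, and a reader who correctly flagged it would be scored as wrong.

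How much this matters depends on how many of the 250 negatives are opposite breasts. The recruitment sentence leaves that open, because it equates 200 women with 395.

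**Working it through.** **1. The recruitment figures (section 8).**
- 150/0.38 = 394.7, so 395, rounded to 400. This reproduces: it is the number to recruit to obtain 150 cancers.
- 150 + 50 = 200 women. This is not 395; it reads as a smallest case set.

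**2. Two routes to 250 negatives.**
- 400 recruits: 400 × 0.38 = 152 cancer and 400 × 0.62 = 248 benign. Opposite breasts needed: 250 − 248 = 2.
- Expected recruitment: 1,920 × 0.25 × 0.62 = 297.6 benign and 1,920 × 0.25 × 0.38 = 182.4 cancer. Opposite breasts needed: none.
- The 150 + 50 minimum: 50 benign breasts plus 150 + 50 = 200 opposite breasts gives 250. Opposite-breast share: 200/250 = 80%.

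The plan states none of these splits, and does not say whether a case is a breast or a woman.

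**3. Effect of k hidden cancers among the 250 negatives.** If a test's readers flag these breasts as they would a biopsied cancer, the AUC of true cancers against them is 0.5. If the readers do not flag them, they score like normal breasts and that test's AUC is unchanged. For a test that flags them:

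AUC′ = (1 − k/250) × AUC + (k/250) × 0.5

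At k = 6:
- bCT: 0.976 × 0.875 + 0.024 × 0.5 = 0.866
- mammography: 0.976 × 0.825 + 0.024 × 0.5 = 0.8172

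The documents do not give k. I assume 1 to 6, which is 0.5% to 3% of 200 opposite breasts.

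| k (assumed) | only bCT flags | both flag | only mammography readers flag |
|---|---|---|---|
| 1 | 0.0485 | 0.0498 | 0.0513 |
| 2 | 0.0470 | 0.0496 | 0.0526 |
| 6 | 0.866 − 0.825 = 0.0410 | 0.866 − 0.8172 = 0.0488 | 0.875 − 0.8172 = 0.0578 |

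Per breast, the gain changes by −0.375/250 = −0.0015, −0.05/250 = −0.0002 or +0.325/250 = +0.0013.

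**4. Power.** The 82% cannot be reproduced, because alpha, sidedness and the variance components are not given. A fixed-reader calculation with four readers, Hanley-McNeil variances, alpha 0.05 and a range of assumed correlations gives 61% to 98% two-sided and 72% to 99% one-sided. The stated 82% lies within both ranges.

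Taking 82% as correct at alpha 0.05 implies a standard error of 0.05/(1.960 + 0.915) = 0.0174 two-sided, or 0.05/(1.645 + 0.915) = 0.0195 one-sided. With that held fixed, the k = 6 gains give power of about 65% to 68% (0.041), 80% (0.0488) and 91% (0.0578).

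**The case against.** Several points on the other side carry weight.

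- **Opposite breasts may hardly be used.** Section 8 calls them available, as an addition. The expected 182 cancers and 298 benign cases fill 150/250 without them, and even the 400-woman floor falls only 2 short. This stands: a reader might infer that 80% of the negatives are unverified, but the 50 + 200 split appears nowhere in the text.
- **The arithmetic slip is one of wording.** A reader might infer that the 400 target or the power is wrong. The documents do not support that: 395 is correct for its purpose, and nothing contradicts the 82%.
- **The direction is not fixed.** It is tempting to say that the bias can only work against bCT, so that a positive result would be safe. Hidden cancers do lie in breasts that the work-up mammogram did not flag, which makes that direction likelier. But the four study readers search the images afresh and are not bound by the clinical report. Specific Aim 4 also records that earlier bCT systems were inferior for microcalcifications and offers parity only as a hypothesis. If only the mammography readers flag such cancers, the apparent gain rises.
- **Benign-biopsy negatives are not a complete cure.** Biopsy verifies a lesion. Under full search, the rest of that breast is also unverified. Using these breasts reduces the risk without removing it.
- **The case mix may be described elsewhere.** Section 8 cites recruitment procedures in a section D3.1 that is not in this document. That is possible, but the protocol still needs its own labelling rule.

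The bilateral, clinically reported MRI narrows the risk for women who have it. It does not settle the matter, because it is optional and is not tied to the label.

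**Conclusion.** The concern holds in a limited form. Followed as written, the plan can score an unverified breast as a negative, its biopsy-for-all-cases rule cannot apply to that breast, and the label depends in part on a test under comparison. The number of negatives affected cannot be derived: it could be none, about 2 or 200 of 250.

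At an assumed six hidden cancers, the planned 0.05 gain becomes 0.041, 0.0488 or 0.0578, depending on which readers flag them. These figures rest on flagged cancers scoring like biopsied ones and unflagged ones like normal breasts.

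I rate this minor to moderate. Aim 4 is neither the primary nor the secondary endpoint in section 6, and the size of the problem is unknown. Against that, the 150 cancers required for Aim 4 drive the 400-woman target.

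**What to change.** 1. **Sample-size text, section 8.** State that about 400 women are recruited to yield about 150 cancers, and give the Aim 4 case set separately. In the power paragraph, state whether a case is a breast or a woman and how the 250 negatives divide between benign-biopsy and opposite breasts.
2. **Truth standard.** Limit biopsy truth to biopsied breasts. Count an unbiopsied opposite breast as negative only after a pre-set period of medical-record follow-up without cancer. Apply the same rule to women with and without MRI, with the MRI report as supporting information only. State in advance how a later cancer is scored.
3. **Reporting.** Give the Aim 4 AUC difference by negative type as a descriptive sensitivity analysis. Under a 50 + 200 split, one stratum would have only 50 negatives, so it should not carry a formal test.

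**Cost.** No added patients, scans or readers, but a longer chart look-up and later final labels. The study team should choose the follow-up length to fit the 5-year timeline. Recruitment runs 48 months and the forgetting time adds 6, so a look-up at month 54 gives F months of follow-up to women enrolled by month 54 − F. With even accrual (assumed), F = 6 keeps all 400; F = 12 keeps 42/48 × 400 = 350. Waiting until month 60 keeps all 400 at F = 12 but leaves no analysis time. Some opposite breasts from late enrollees would be lost, possibly after they had been read.

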**Specific Aim 5: High Risk Screening Performance: CE breast CT and CE-breast MRI.**  
To evaluate the potential of CE-bCT for use in high risk screening (as MRI is used now), CE-bCT ROC performance will be compared against CE-MRI ROC performance. Radiologists will perform full 3D search of the CT and MRI (independently) volume data sets (both with and without contrast) and report

overall probability of malignancy for each modality. Location-specific metrics for potential FROC or LROC analysis will also be captured. Assessment of  $\Delta$ HU will also be performed to quantitatively evaluate predictive performance for malignancy.

Specific Aims 1 and 2 do not require changes in hardware; these two aims are completely focused on post-acquisition image processing techniques (software). Therefore, accrual to the clinical trials as described in Aim 3 can commence on day one of this project. The acquired projection image data from the scanner is always saved, and once the scatter-correction and flat fielding techniques (Aim 1) and optimized reconstruction methods (Aim 2) are finalized, images will be re-reconstructed and become available for the ROC studies on normal-risk screening (Aim 4) and high-risk screening (Aim 5) performance. We believe that this 5 year study will demonstrate that non-contrast bCT can outperform 2D & 3D mammography in breast cancer screening for normal risk patients, and that CE-bCT is (at least) equivalent to CE-MRI for screening high-risk women.

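### Aims 4 and 5 are sized with a fixed-effects model, most naturally read as conditional on four readers, while general conclusions are expected: label the power, and add a supportive random-reader analysis or limit the scope

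*Combined protocol and SAP*

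**What the plan says.** Section 8, under *Numbers of patients needed*, says that the power analyses were run "for a fixed effects ANOVA model instead of the usual mixed effects model", and names the mixed-effects (DBM) and Obuchowski-Rockette models as the alternatives not used. That sentence covers both reader studies. For Aim 4, "we have sized the study on the basis of 4 readers, an improvement of 0.05 in AUC"; the AUCs are 0.825 and 0.875, and 82% power is given for 150 positive and 250 negative cases. For Aim 5 the same approach gives 82% with 4 readers and 60 positive plus 90 negative cases, judged by whether the observed difference exceeds -0.025. The section gives no alpha, sidedness or variance components, and does not say which factor is fixed.

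Section 2, Specific Aim 4, describes the final analysis only in outline: "digital mammography and non-contrast bCT images will be compared in a standard receiver operating characteristic (ROC) study". It names no reader model. The last paragraph of section 2 then states: "We believe that this 5 year study will demonstrate that non-contrast bCT can outperform 2D & 3D mammography in breast cancer screening". The same sentence expects contrast-enhanced bCT to be at least equivalent to contrast-enhanced MRI in high-risk women. No section confines either conclusion to the study's readers or plans a random-reader analysis.

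**The concern.** A test that holds readers fixed asks whether these four readers, on average, did better with one modality. A statement about screening performance concerns readers in general. The two questions have different variances as soon as the true AUC difference varies from reader to reader. The extra term depends on the number of readers, so more cases do not shrink it. The hope of exceeding the minimum ("At a minimum, we plan to recruit 400 and will strive to recruit substantially more") therefore does not remove it.

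Two things are at stake. If the final test also treats readers as fixed and its result is carried to the general claim, the false-positive rate for that claim exceeds the nominal level. If a random-reader test is used instead, the printed 82% does not describe its power. With no reader model named for the final analysis, the choice could also be made after the ratings have been seen.

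**Working it through.** **Inputs from section 8.** J = 4 readers, AUC difference 0.05 (0.825 versus 0.875), 150/250 cases, power 82%.

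**Assumptions, not in the documents.**
- Two-sided 5% test.
- The sizing simulation contained no reader-by-modality variance.
- tau, the between-reader SD of the true AUC difference, is 0 to 0.03.
- c, the share of the fixed-reader variance that is common across readers, is 25% to 75%.

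**Step 1: is 82% plausible for fixed readers?** It cannot be reproduced uniquely, because the correlations are not given. The Hanley-McNeil SE of a single AUC at 150/250, averaged over the two AUCs, is 0.0214. The fixed-reader variance of the difference is (2/J) × s² × [(1 - r1) + (J - 1)(r2 - r3)]. With assumed correlations 0.3, 0.4 and 0.2 this is 0.5 × 0.0214² × 1.3, so SE = 0.0172 and power = Phi(0.05/0.0172 - 1.960), about 82.7%. Other assumed correlations gave 62-96%. The printed figure is therefore plausible. For this set c = 4 × 0.2/1.3 = 0.62, inside the range used below.

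**Step 2: SE implied by 82%.** 0.05/(1.960 + 0.915) = 0.0174, a variance of 0.000302. (At one-sided 5% the SE would be 0.0195; the figures below are two-sided.)

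**Step 3: variance for the general claim.** V = 0.0174² + tau²/4.

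**Step 4: type I error if readers are held fixed but the claim is general.** This is 2 × [1 - Phi(1.960 × 0.0174/√V)].

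| tau | √V | 1.960 × 0.0174/√V | type I error |
|---|---|---|---|
| 0 | 0.0174 | 1.960 | 5.0% |
| 0.01 | 0.0181 | 1.884 | 6.0% |
| 0.02 | 0.0201 | 1.699 | 8.9% |
| 0.03 | 0.0230 | 1.484 | 13.8% |

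**Step 5: power of a random-reader test on the same ratings.** I used the Obuchowski-Rockette F test with Hillis degrees of freedom. The share of V that rests on the reader-by-modality mean square is w = [(1 - c) × 0.0174² + tau²/4]/V. Then df = (J - 1)/w² = 3/w², and the noncentrality is 0.05²/V.

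| tau | noncentrality | df at c = 25% / 75% | power at c = 25% / 75% |
|---|---|---|---|
| 0 | 8.27 | 5.3 / 48 | 65% / 80% |
| 0.01 | 7.64 | 5.1 / 31.8 | 61% / 76% |
| 0.02 | 6.21 | 4.5 / 15.7 | 50% / 65% |
| 0.03 | 4.74 | 4.1 / 9.2 | 39% / 50% |

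Power is below 82% even at tau 0, because four readers leave few denominator degrees of freedom. A normal approximation misses this and would be too favourable.

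**Cross-check of direction.** A Roe-Metz-type simulation with assumed components (500 runs per setting) gave fixed-reader type I error of 3-6% with no reader-by-modality variance. With variances of 0.005 to 0.03 on the latent scale it gave about 9-41%, against about 4-7% for the random-reader test. These latent-scale values do not map one-to-one onto tau.

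Aim 5 was not recomputed. Its success rule is set on the observed difference, but the question of scope is the same.

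**The case against.** The choice is disclosed: section 8 names the usual models and says that they were not used for sizing. It rests on a cited power analysis that is not available here. The simulation may have included reader-by-modality variance, in which case the figures above overstate the loss. The closing sentence of section 2 states a belief, not a decision rule. Aim 4 is not among the endpoints in section 6, where safety and comfort are primary and "The secondary study endpoint will be the comparison of breast MRI versus breast CT in terms of sensitivity and specificity". A random-reader test with four readers may also be too weak to carry a general claim.

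All of this stands, and it keeps the point modest. It does not close the gap: the only reader model on record is the fixed-effects one, and no section matches the scope of the conclusions to it. Aim 4 is also the comparison sized at 150 positive and 250 negative cases, the larger of the two studies.

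A reader might infer three stronger things that the documents do not support:
- That the 82% is wrong. Nothing shows this for a conclusion about these four readers.
- That Aim 4 is demonstrably underpowered. tau and the common-variance share are not reported, and recruitment may exceed the minimum ("we would expect to be able to acquire 182 cases" with cancer, against 150 needed).
- That type I error is inflated as planned. The final test is not specified, so this is conditional on its also holding readers fixed.

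**Conclusion.** The point holds as an inexpensive improvement, not as an error in the sample size. Both reader studies are sized on a model most naturally read as conditional on four readers, while the conclusions expected of them are general. Under the stated assumptions, a fixed-reader Aim 4 test carried to the general claim would have a type I error of about 6, 9 or 14% at tau 0.01, 0.02 or 0.03. A random-reader test would have power between about 80% (tau 0, c = 75%) and 39% (tau 0.03, c = 25%). These sizes are illustrations. The mismatch of scope does not depend on them, but its practical weight does.

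**What to change.** - In section 8, label the 82% as power conditional on the four readers, or state that reader-by-modality variance was included, if it was. Give the alpha and sidedness.
- Keep the fixed-reader analysis as the sized analysis.
- Prespecify, for Aims 4 and 5, a supportive random-reader, random-case analysis (Obuchowski-Rockette or DBM, with Hillis degrees of freedom) of the same ratings, reported beside the fixed-reader result.
- In section 2 (Aims 4 and 5 and the closing paragraph), limit the conclusions to these four readers unless the random-reader analysis also supports them.
- If random-reader power is shown, compute it from that F test, not from a normal test, and mark it as assumption-based. The Step 5 table can serve for Aim 4.

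The cost is a few sentences and one further analysis per aim, with no new readers, cases or readings. The drawback is a less favourable power figure and a wider interval for the general claim, which four readers may not be able to establish. Limiting the scope avoids this but gives up that claim.
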